8.2.1.5 Pregnancy

- If a female becomes pregnant during the study, the Investigator should stop the study drug. The 1097
- Investigator shall instruct the subject to notify her physician of the study drug. Best practices should be 1098
- followed in order to ensure the welfare of the subject and the fetus. The subject will continue to be 1099
- followed as part of the ITT population, but the pregnancy will be documented as a protocol deviation. 1100
- 1101 The subject will not be evaluated as part of the PP population for timepoints after the pregnancy is
- confirmed. 1102

1103			
1104	Pregnancy by itself will not be considered an AE or serious adverse event (SAE). Hospitalization for a		
1105	normal delivery does not constitute an SAE. However, the occurrence of an adverse pregnancy outcome		
1106	for the mother or child may constitute an AE or SAE, and these should be reported as AE. Reporting of		
1107	all pregnancies to Novo Nordisk should occur within 5 working days from the time the investigator		
1108	becomes aware of the event.		
1109	8.2.2 Reporting of Serious Adverse Events and Unanticipated Problems		
1110	Investigators must conform to the adverse event reporting timelines, formats and requirements of the		
1111	various entities including Novo Nordisk, but at a minimum those events that must be reported are those		
1112	that are:		
1113	 related to study participation, 		

- unexpected,
 - serious or involve risks to subjects or others, and
- 1116 serious adverse events

1114

1115

For Narrative Reports of Safety Events

- 1119 If the report is supplied as a narrative, the minimum necessary information to be provided at the time of the initial report includes: 1120
 - Study identifier
 - Study Center
 - Subject number
 - A description of the event
 - Date of onset

- Current status
- Whether study treatment was discontinued
- The reason why the event is classified as serious
- Investigator assessment of the association between the event and study treatment

1121 8.2.2.1 Investigator reporting: notifying the IRB

1122 Report Promptly, but no later than 5 working days:

1123 Researchers are required to submit reports of the following problems promptly but no later than 5 working days from the time the investigator becomes aware of the event: 1124

Unanticipated problems including adverse events that are unexpected and related

- Unexpected: An event is "unexpected" when its specificity and severity are not accurately reflected in the protocol-related documents, such as the IRB-approved research protocol, any applicable investigator brochure, and the current IRB-approved informed consent document and other relevant sources of information, such as product labeling and package inserts.
- Related to the research procedures: An event is related to the research procedures if in the opinion of the principal investigator, the event was more likely than not to be caused by the research procedures.
- Harmful: either caused harm to subjects or others, or placed them at increased risk

1133 1134 1135

1136

1137

1138

1139

1140 1141

1142

1125

1126

1127

1128

1129

1130

1131 1132

Other Reportable events:

The following events also require prompt reporting to the IRB, though **no later than 5 working days**:

- Complaint of a research subject when the complaint indicates unexpected risks or the complaint cannot be resolved by the research team.
- Protocol deviations or violations (includes intentional and accidental/unintentional deviations from the IRB approved protocol) for any of the following situations:
 - o one or more participants were placed at increased risk of harm
 - the event has the potential to occur again

- o the deviation was necessary to protect a subject from immediate harm
- Breach of confidentiality
- **Incarceration of a participant** when the research was not previously approved under Subpart C and the investigator believes it is in the best interest of the subject to remain on the study.
 - New Information indicating a change to the risks or potential benefits of the research, in terms of severity or frequency. (e.g. analysis indicates lower-than-expected response rate or a more severe or frequent side effect; Other research finds arm of study has no therapeutic value; FDA labeling change or withdrawal from market)

Reporting Process

1147

1148

1149

1150 1151 1152

1153

1154

1155 1156

1157

1160

1164

1166

1167

1168

1170

1173

1178

1183

The reportable events noted above will be reported to the IRB using the form: "Reportable Event Form" or as a written report of the event (including a description of the event with information regarding its fulfillment of the above criteria, follow-up/resolution and need for revision to consent form and/or other study documentation).

1158 Copies of each report and documentation of IRB notification and receipt will be kept in the Clinical Investigator's study file.

8.2.2.2 AE Reporting to Novo Nordisk

The investigator will report to Novo Nordisk all SAEs, SUSARs, and SADRs at the same time such events are reported to regulatory authorities or within 15 days from the investigator becoming aware of such adverse events, whichever comes first.

The investigator will collect the following information at minimum for each of these events:

- Study name
- Patient identification (e.g. initials, sex, age)
- Event (preferably a diagnosis)
- 1169 Drus
 - Reporter identification (e.g. Name, or initials)
- Causality
- 1172 Outcome

8.2.3 Follow-up of Adverse Events

- During and following a subject's participation in a clinical trial, the investigator and institution will provide adequate medical care to the study subject for any study-related adverse events, including clinically significant laboratory values related to the study. State that this medical care for study subjects will be provided regardless of their insurance status.
- All adverse events classified as serious or severe or possibly/probably related to the trial product must be followed until the subject has recovered and all queries have been resolved. For cases of chronic conditions follow-up until the outcome category is "recovered" is not required, as these cases can be closed with an outcome of "recovering" or "not recovered".
- All other adverse events must be followed until the outcome of the event is "recovering" (for chronic conditions), or "recovered" or until the end of the post-treatment follow-up stated in the protocol, whichever comes first, and until all queries related to these AEs have been resolved.

1187 8.3 Liability 1188 The sponsor-investigator will be responsible for the conduct of the study and agrees to defend, indemnify, and hold harmless Novo Nordisk, any of its parent companies, affiliates, or subsidiaries, and their 1189 respective officers, directors, employees, agents, representatives, distributors, salespersons, customers, 1190 licensees, and end-users from and against any claim, suit, demand, loss, damage, expense or liability 1191 imposed by any third party arising from or related to: (a) any breach of sponsor-investigator's obligations 1192 or representations; or (b) sponsor-investigator's negligent or grossly negligent use or willful misuse of the 1193 1194 study drug, the results, or services derived therefrom. This indemnification shall not apply in the event and to the extent that a court of competent jurisdiction or a duly appointed arbiter determines that such 1195 losses or liability arose as a result of Novo Nordisk's gross negligence, intentional misconduct, or 1196 1197 material breach of its responsibilities 1198 8.4 **Unblinding Procedures** 1199 The randomization information will be revealed to the investigator only in a medical emergency, i.e. 1200 when this appears necessary to ensure the subject's safety and would be instrumental in further treatment 1201 decisions. 1202 1203 If a subject's treatment is unblinded, details of the time and reason for revealing must be documented in the subject's medical records and in the CRF and should be reported to DSMB in 48 hours. 1204 1205 8.5 **Stopping Rules** 1206 • The trial will be terminated if two or more patients die within the 30 days of study drug 1207 administration 1208 • The trial will be terminated if during the follow-up period five or more of the first 50 patients 1209 developed gastrointestinal or endocrine disorder leading to inpatient admission. 1210 • The trial will be terminated if the DSMB determine that the study should be terminated. 1211 8.6 **Medical Monitoring** 1212 It is the responsibility of the Principal Investigator to oversee the safety of the study. This safety 1213 monitoring will include careful assessment and appropriate reporting of adverse events as noted above, as well as the construction and implementation of a site data and safety-monitoring plan. 1214 1215 8.6.1 **Data Monitoring Committee** 1216 1217 **Data Safety and Monitoring Board (DSMB)** 1218 8.6.1.1 DSMB Responsibilities Review the research protocol, informed consent documents, and plans for data safety; 1219 1220 Review the following blinded data; baseline data 1221 1222 safety data (mortality and morbidity) o efficacy data 1223 1224 study withdrawal due to non-compliance and AEs major protocol violation 1225 • Review external data to the study when relevant information that may have an impact on 1226 subject safety becomes available; 1227 Review and evaluate ad hoc safety issues concerning the study at the request by study team; 1228

1229

and

Make recommendations to the investigators concerning continuation, termination, or other
 modifications of the study based on the observed beneficial or adverse effects of the study.

1232 1233

1234

1235

1236

1237

1238

All DSMB members will disclose their conflicts of interests before the study initiation and any updates during the study period.

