476 will be discontinued after consulting with the subject's primary physician/endocrinologist. 477 Patients taking an insulin secretagogue (eg, sulfonylureas) will be informed of the 478 increased risk of hypoglycemia associated with co-administration of the study drug 479 and instructed to notify the investigators of any symptoms of hypoglycemia. 480 If the subject is a female of childbearing potential (sexually active and not sterile nor 481 postmenopausal for at least 1 year), have a negative pregnancy test within 4 weeks 482 prior to study commencement, and then at 3, 6, and 9 months. 483 Use of reliable contraception will be assessed during the study period. 484 DSMB reviews all AEs including SAEs and provides the appropriate 485 recommendations 486 487 1.6.2 **Potential benefits** It is hypothesized that this study drug will help the subject lose weight and decrease the incidence 488 or severity of weight related co-morbidities. In addition, the medical community and society 489 490 stand to benefit from a better understanding of the efficacy and safety of the study drug post-RYGB. 491 2 492 **Study Objectives** 493 2.1 **Primary Objective** 494 The primary objective of this study is to assess the utility of liraglutide to reverse weight regain versus placebo in patients at least 18 months following RYGB who are experiencing weight regain. 495 496 2.2 **Secondary Objective** The secondary objectives of this study are to assess the efficacy of liraglutide in improving 497 cardiometabolic risk profile (as indicated by serum lipids, HbA1c, and waist circumference) and quality 498 of life (as assessed by PHO-9 (Patient Health Questionnaire), versus placebo in patients at least 18 499 months following RYGB who are experiencing weight regain, as well as the safety of liraglutide in this 500 patient population. 501 3 **Study Design** 502 503 3.1 **Research Design and Methods** The specific aims of this proposal are: 504 To evaluate the effects of liraglutide on body weight loss in patients who are experiencing weight 505 506 regain following RYGB. We will perform a randomized, double-blinded, placebo-controlled trial of liraglutide 507 versus placebo over a follow-up period of 12 months. 508 We hypothesize that the liraglutide group will contain a significantly greater 509 proportion of patients achieving at least 5% loss of pre-randomization body 510 weight at 12 months, than the placebo group. 511 To evaluate the effects of liraglutide on cardiometabolic risk and quality of life in patients who 512 are experiencing weight regain following RYGB. 513 We will perform a randomized, double-blinded, placebo-controlled trial of liraglutide 514 515 versus placebo over a follow-up period of 12 months.

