
516517

We hypothesize that the liraglutide group will demonstrate greater improvement

in cardiovascular risk profile (as assessed by serum lipids, HbA1c, and waist

518	circumference) and quality of life (as assessed by the PHQ-9) at 12 months, than
519	the placebo group.
520	 To evaluate the safety of liraglutide in post-RYGB subjects.
521	o We will monitor adverse events, blood counts and serum chemistries in subjects
522	receiving liraglutide or placebo over a period of 12 months.
523	We hypothesize that the liraglutide group will exhibit more frequent
524	hypoglycemia and elevations in lipase and amylase, but that these episodes will
525	be clinically insignificant.
526	• To evaluate the changes in obesity-related comorbid conditions in patients who are experiencing
527	weight regain following RYGB.
528	 We will monitor obesity-related comorbid conditions in subjects receiving liraglutide or
529	placebo over a period of 12 months.
530	 We hypothesize that the liraglutide group will exhibit improvements in obesity-
531	related comorbid conditions (hyperglycemia, hyperlipidemia, blood pressure, and
532	obstructive sleep apnea) at 12 months, than the placebo group.
533	3.2 Endpoints
534	• Primary Endpoint: Proportion of subjects losing at least 5% of enrollment body weight at 12 months.
535	• Secondary Endpoints: Fasting serum glucose, HbA1c, LDL-cholesterol, HDL-cholesterol,
536	triglycerides, waist circumference, blood pressure, STOP-BANG score, PHQ-9
37	• Primary and secondary endpoints will be assessed at clinic visits prior to randomization and at 3, 6, 9
538	and 12 months post-first study drug administration.
539	3.3 Study Type
540	Randomized, single-center, double-blind, placebo-controlled study with two arms. Randomization will
541	be 2:1 (drug:placebo) with stratification by gender and percent post-operative TBWL (25%, 25 – 49.9%).
542	3.4 Rationale for study Design
543	A randomized, placebo-controlled study design was chosen as this is the methodology that will best
544	assess the efficacy of liraglutide for weight loss in the post-RYGB population. 2:1 randomization was
545 546	chosen with the intention of increasing potential participant interest given better than even odds of
547	randomization to liraglutide.
548	A single-center study was chosen given that the NYU Langone weight management program has a pool
549	of 700 post-RYGB patients in our retrospective database, and that recent data from our program suggests

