8.6.1.4 Meeting Format

are too high to continue the study enrollment

 DSMB meetings will generally be conducted by face to face or teleconference and facilitated by the DSMB chair. The investigator and study coordinator will attend the meeting with DSMB members to provide additional information requested or answer the questions raised during the review of the data.

All Adverse Events Report including expected and unexpected will be recorded and reported to DSMB using Excel and SPSS program. The AE reports will not contain any information that can potentially disclose any subject's treatment group. AE reports will include the followings.

1294	 Name of event 		
1295	Onset and end date		
1296	• UAE		
1297	• Severity (mild, moderate, severe)		
1298	• Seriousness		
1299	 Relationship to the study drug/procedure 		
1300	Action taken		
1301	• Outcomes		
1302			
1303	All reports will be submitted by the study coordinator.		
1304	r.		
1305	Meeting Minutes: Minutes of DSMB meetings will be distributed to members, all investigators, and		
1306	study personnel within 4 weeks and also to IRB annually if available.		
1307	Minutes include at a minimum:		
1308	 Protocol number and study title 		
1309	DSMB meeting date		
1310	Copy of agenda		
1311	• A list of attendances, including DSMB members and any other people present, listing their		
1312	professional title and role at the meeting		
1313	 Information reviewed and related discussion during the meeting 		
1314	 DSMB recommendations including clear and concise rationale 		
1315			
1316	Communications		
1317	The DSMB chair communicates directly with the investigators to allow them the opportunity to ask		
1318	questions and discuss any recommendations. If the investigator(s) accepts the recommendations of the		
1319	DSMB, the investigator(s) will be responsible for implementing the actions in response. In the event the		
1320	study must be amended, the investigator will prepare and submit the amendment to the DSMB for		
1321	approval prior to implementing amendment changes.		
1322	8.6.1.5 Reportable Adverse Events		
1323	All SAEs will be reported to all DSMB member and all investigators via e-mail within one or two		
1324	working day of learning of the event. A summary of all adverse events, (previously reported or not,		
1325	serious or not) will be submitted to the DSMB as described in this plan.		
1326	Serious of not) will be successful to the Borne to the successful to the plant		

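### As written, the DSMB's reporting route provides no comparison of safety by arm, although the board must advise on observed adverse effects

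*Combined protocol and SAP*

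**What the plan says.** **What the board receives.** Section 8.6.1.1 has the board "Review the following blinded data", and lists baseline, safety and efficacy data, withdrawals and major violations. The schedule in 8.6.1.3 names safety data at all four reviews without a breakdown by arm.

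**How the reports are made.** Section 8.6.1.4 says "The AE reports will not contain any information that can potentially disclose" any subject's group. Its eight report fields include no arm or coded arm. It adds: "All reports will be submitted by the study coordinator". Under 5.6.1 the randomization lists go to the pharmacist, and the rest of the study staff are blinded.

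**Who is present.** Also in 8.6.1.4: "The investigator and study coordinator will attend the meeting with DSMB members". No closed session is described. "Minutes of DSMB meetings will be distributed to members, all investigators, and" study personnel.

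**What the board must do.** Section 8.6.1.1 asks for recommendations on continuation, termination or "modifications of the study based on the observed beneficial or adverse effects of the study". Section 8.6.1.6 lets the board justify termination by its own analysis of an overwhelming safety issue. Section 1.6.1 counts the board among the measures that reduce risk: "DSMB reviews all AEs including SAEs and provides the appropriate" recommendations.

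**The concern.** Judging whether a drug is causing harm requires a comparison with placebo. Many of the expected events are common: section 1.6.1 lists nausea at 39.3% and diarrhea at 20.9%. A pooled total therefore says little about cause. If the route in the protocol is followed as written, the person who prepares the reports does not know the allocation, and no one else is assigned to add it. The board would then advise from totals and single cases. It could miss an excess on drug, or blame the drug for a high total when the arms are alike. What is at stake is the quality of safety oversight. The trial's error rates are not affected.

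**Working it through.** **1. Trace the route.** No figure in the plan has to be reproduced here, because the point rests on the text.
- Source of the reports: the study coordinator (8.6.1.4).
- The coordinator's knowledge of allocation: none, since only the pharmacist holds the lists (5.6.1).
- Content of AE reports: nothing that reveals a subject's group, and no arm field (8.6.1.4).
- Allocation-related item sent to the board: notice, within 48 hours, of an individual emergency unblinding (8.4).
- Other inputs: SAE e-mails within one or two working days (8.6.1.5), ad hoc meetings (8.6.1.3) and the 8.5 rules. These concern single cases or pooled counts.

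No step in this chain yields a table by arm.

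**2. What a pooled count can tell the board.** Inputs: 2:1 allocation (3.3, 7.1), so 50 subjects split about 33:17, and the 8.5 rule of five or more of the first 50 admitted for a gastrointestinal or endocrine disorder. The admission rates are assumptions. The probability of triggering is P(X + Y ≥ 5), with X ~ Bin(33, p_drug) and Y ~ Bin(17, p_placebo).

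| Drug | Placebo | Pooled rate | P(trigger) |
|---|---|---|---|
| 6% | 6% | 6.0% | 0.179 |
| 8% | 2% | (33×0.08 + 17×0.02)/50 = 5.96% | 0.175 |
| 9% | 0% | 33×0.09/50 = 5.94% | 0.171 |

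The rule responds to the pooled rate and barely separates no drug effect from all events being on drug.

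**3. The same total with different splits.** Take 8 events among 50 subjects.
- 8:0 gives 8/33 = 24.2% versus 0/17 = 0%. With no drug effect, the probability that all 8 fall on drug is C(33,8)/C(50,8) = 0.026; two-sided Fisher p = 0.039.
- 5:3 gives 5/33 = 15.2% versus 3/17 = 17.6%; Fisher p = 1.0.
- With no effect, 8×33/50 = 5.28 events are expected on drug.

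A pooled report shows 8 in both cases.

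**4. What a coded table would add.** The measure is the exact probability that a two-sided Fisher test gives p < 0.05 with the higher rate on drug, summed over the two binomials. The event rates are assumptions.

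| Table size (drug:placebo) | 11% vs 2% | 20% vs 2% | 30% vs 2% |
|---|---|---|---|
| 33:17 | 0.017 | 0.25 | 0.68 |
| 45:22 | 0.075 | 0.50 | 0.86 |
| 88:44 | 0.33 | 0.89 | 0.997 |

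The second row is the review at 50 completers under the plan's 25% loss: 50/0.75 = 66.7, or about 67 subjects. The third row assumes that all 132 are enrolled by the review: 132×2/3 = 88 on drug.

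**The case against.** **Missing and delegated text.** The part of the DSMB section between 8.6.1.1 and 8.6.1.3 was not available to this review. Section 8.6.1.3 leaves report formats and termination guidelines to a first DSMB meeting before enrollment, and 8.6 calls for a separate site data and safety-monitoring plan. Any of these could provide coded tables. This stands, and it limits the point to what the available text provides.

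**Blinded need not mean pooled.** A reader might infer that the protocol forbids the board any by-arm view, or contradicts itself. The documents do not support that. Data coded by arm are still blinded data, and the bar in 8.6.1.4 is worded for AE reports and the individual subject's group. An aggregate coded table is not excluded. It is simply not provided for, and the person named to submit reports could not make one.

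**Section 3.1.** It is tempting to cite the safety hypothesis, "We hypothesize that the liraglutide group will exhibit more frequent" hypoglycemia and enzyme elevations, as a comparison the board must monitor. It is a 12-month study aim for the final analysis, and the same sentence expects these episodes to be clinically insignificant. The point does not rest on it.

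**Efficacy data and 7.4.** A reader might also see a conflict between the board's efficacy review and the absence of planned interim efficacy analyses. Looking at blinded efficacy data is not such an analysis, and the only termination ground that 8.6.1.6 names is safety. No change is needed there.

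**Weak detection and existing safeguards.** For increased lipase, listed at 5.3% in 1.6.1, against an assumed placebo rate of 0 to 2%, the chance of a flag is below 0.001 at 33:17 and 0.018 to 0.044 at 88:44. A 5:0 split at 33:17 gives only p = 0.15. SAE e-mails, ad hoc meetings and the stopping rules do exist, and the dose is one that 1.5 describes as approved for weight loss. This lowers the expected gain, but none of these safeguards compares the arms.

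**Conclusion.** The point holds in limited form. In the available text, the route to the board yields no safety comparison by arm, while the board is asked to advise on adverse effects and may terminate on its own safety analysis. Under the assumed rates, the pooled five-of-50 rule triggers with almost the same probability (0.171 to 0.179) whether the arms are alike or all admissions are on drug.

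The benefit of a coded table is modest early and grows with enrollment: for 20% versus 2%, the chance of a flag rises from 0.25 at 33:17 to 0.89 at 88:44. These figures rest on assumed event rates and on splits close to 2:1. The conclusion would change if the unseen DSMB text, the formats set at the first meeting or the site plan already provide coded tables. This is a worthwhile, inexpensive improvement in oversight. It does not show an error in the trial's analysis.

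**What to change.** - In 8.6.1.1, state what blinded means for the board's data.
- In 8.6.1.1 and 8.6.1.4, provide aggregate safety tables by coded arm: AEs and SAEs by term, hypoglycemia, lipase, amylase and withdrawals.
- The coordinator supplies the safety data without arm. The pharmacist who holds the randomization list adds the code and sends the tables directly to the board.
- The board reviews them in a closed session without the investigator and coordinator, and they stay out of the circulated minutes.
- Event-level AE reports stay as they are.

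The cost is protocol and DSMB wording, plus a small reporting task for the pharmacist at each review that the protocol does not now assign. Visits, endpoints and sample size are unchanged. There are two downsides. The 2:1 group sizes will reveal to the board which code is drug; the study team stays blinded if the tables bypass the coordinator and the minutes. At about 50 subjects only large imbalances would be clear, and chance splits across many AE terms could mislead, so the tables should be labeled descriptive.
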